- The principal investigator of this study is qualified to serve as P.I. and has the support of the hospital for this research project.

YNHH HSPA Name (PRINT) and Signature

Date

SECTION V: RESEARCH PLAN

1. **Statement of Purpose:** State the scientific aim(s) of the study, or the hypotheses to be tested.

Ketamine is an anesthetic agent, recently found to exert a rapid and potent antidepressant effect in severely depressed patients. Mounting evidence indicates that a ketamine-induced surge in glutamate neurotransmission, particularly in the frontal cortex, plays a crucial role in the antidepressant and psychotomimetic effects of the drug. Our preliminary data also suggests ketamine has a normalizing effect on long-range neural dysconnectivity in Major Depressive Disorder (MDD), and that these changes in functional connectivity, as measured by resting state functional MRI (rs-fMRI), are related to the antidepressant effect of the drug.

A better understanding of the mechanism of neuropsychiatric effects of ketamine are critically important, as pharmacological modulation of these effects can assist in the development of new medications for the treatment of multiple psychiatric disorders including depression and schizophrenia. The aims of the current proposal are to provide insight into (a) the impact of ketamine on functional connectivity as measured by rs-fMRI; (b) the relationship between rs-fMRI alterations and ketamine-induced neurochemical changes in glutamate; and (c) to investigate the influence of a glutamate release inhibitor (i.e., lamotrigine) on these ketamine-induced neural alterations in healthy volunteers using safe, minimally invasive, state-of-the-art multi-modal neuroimaging and behavioral assessment. Further examination of the effects of ketamine-induced changes in neural connectivity as well as the impact of a pre-treatment dose of lamotrigine can provide key insight into the role of glutamate and the mechanism of ketamine's rapid antidepressant and perceptual effects and its influence on neural connectivity.

- **Aim 1:** To characterize the effects of a single, sub-anesthetic dose of ketamine in rs-fMRI in healthy subjects.
Design: Twenty-four healthy participants will be randomized into one of two parallel groups—ketamine+lamotrigine or ketamine+placebo—and will complete pre- and post-ketamine rs-fMRI.

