Hypothesis 1: Post-ketamine rs-fMRI data will demonstrate a pattern of increased global brain connectivity (GBC) in fronto-temporal cortex.
- **Aim 2:** To examine the relationship between ketamine-induced glutamate alterations and changes in rs-fMRI of healthy subjects.
Design: Using MRS we will measure alterations in glutamate levels during ketamine infusion and correlate this data to rs-fMRI changes.
Hypothesis 2: Ketamine-induced glutamate alterations will positively correlate with changes in GBC.
- **Aim 3:** To examine the effect of administering a glutamate release inhibitor, lamotrigine, prior to ketamine infusion on neural network configuration and connectivity.
Design: Participants will be randomized to receive 300 mg oral lamotrigine or a matched-placebo medication 2-hours prior to ketamine infusion.
Hypothesis 3: Lamotrigine will attenuate the effect of ketamine-induced GBC enhancement in the neural network.

2. **Background:** Describe the background information that led to the plan for this project. Provide references to support the expectation of obtaining useful scientific data.

Ketamine

Major Depressive Disorder (MDD) is a leading cause of disability worldwide ¹, with a 21-fold increase of suicide attempts during major depressive episodes ². In the United States, the estimated lifetime prevalence is approximately seventeen percent ³. While more than 20 antidepressant medications are currently available, the efficacy of these medications is limited ⁴⁻⁷. Moreover, traditional antidepressants, all of which target the monoaminergic system, take weeks to months to reach their full clinical effects ⁸. Hence, there is an urgent need for a novel class of antidepressants that can offer (1) rapid acting effects and (2) efficacy in patients not achieving adequate benefit from existing medications. Over the last decade, accumulating evidence has shown that low dose of ketamine, a *N*-methyl-D-aspartate (NMDA) receptor antagonist, may possess both of these properties ⁹.

NMDA receptor dysfunction has been implicated in the pathophysiologic processes of depression, schizophrenia, and other psychiatric illnesses ^{10,11}. Ketamine is now the prototype for a new generation of antidepressants that rapidly alleviates depression and demonstrates efficacy even in patients with symptoms that are refractory to currently available treatments. The association between glutamate alterations and psychotomimetic effects of ketamine in human has been suggested

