proposal, we will implement state-of-the-art multi-modal neuroimaging methods to examine the role of ketamine-induced glutamate alterations on connectivity in rs-fMRI, the relationship between the alterations in connectivity and glutamate changes, and the impact of lamotrigine, a glutamate inhibitor. This will provide critical information concerning the impact of ketamine on neural connectivity and use of lamotrigine will allow us to confirm target engagement and the impact of blocking the glutamate system, furthering our understanding of the mechanisms of action and the role of glutamate in ketamine's effects. Moreover, given the well-characterized similarity between ketamine's acute psychotomimetic effects and psychosis ¹⁰, our ongoing studies are highly significant since the specific data generated with ketamine can equally contribute to the understanding and drug development of mood disorder and schizophrenia, devastating mental illnesses affecting millions of patients around the world ¹.

3. **Research Plan:** Summarize the study design and research procedures using non-technical language that can be readily understood by someone outside the discipline. Be sure to distinguish between standard of care vs. research procedures when applicable, and include any flowcharts of visits specifying their individual times and lengths. Describe the setting in which the research will take place.

A. Overview: In this study, 32 healthy participants will be randomized into one of two parallel groups: (a) open-label ketamine and active lamotrigine, or (b) open-label ketamine with a matched-placebo control (i.e., sugar pill). All participants will complete a baseline rs-fMRI approximately 1-week prior to the ketamine infusion and a follow-up rs-fMRI 24-hours post-infusion. The subanesthetic dose of ketamine (0.23mg/kg bolus followed by 0.58mg/kg infusion over approximately 60 minutes) will be administered via intravenous infusion to occur during the MRS scan. Participants will be administered lamotrigine (300 mg oral dose) or the matched-placebo control about 2-hours prior to the start of the infusion.

B. Experimental Subjects: Twenty-four healthy subjects between the ages of 21-65 years will be recruited for this study through advertising and referral from clinics in the community. Subjects will complete an informed consent process and will be thoroughly screened for inclusion and exclusion criteria as described below.

B.1. Restrictions

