Subjects will be advised not to drive or operate heavy machinery for at least 24-hours after completing the infusion.

Subjects will be asked to refrain from alcohol use for one-week prior to each MRS session.

Subjects must agree to use a barrier method (e.g., condom) as contraception for a 2-week period following the study drug.

Subjects will be advised to refrain from undergoing any elective surgeries, including dental work, for a 2-week period following the study drug.

B.2. Discontinuation of subjects

Criteria for discontinuation

Subjects may be discontinued from study treatment and assessments at any time. Specific reasons for discontinuing a subject from this study are:

- Voluntary discontinuation by the subject, who is at any time free to discontinue his/her participation in the study without prejudice to further treatment.
- Adverse reaction to ketamine or lamotrigine.
- Inability to complete MR studies due to claustrophobia or other.
- Stopping birth control or positive pregnancy test.
- Safety reasons as judged by the investigator.
- Severe non-compliance to protocol as judged by the investigator.
- Incorrect enrollment (i.e., the subject does not meet the required inclusion/exclusion criteria for the study).

Subject lost to follow-up.

A subject that discontinues will always be asked about the reason(s) for discontinuation and the presence of any adverse events. If possible, they will be seen and assessed by the investigator. Adverse events will be followed up as medically necessary.

C. Pre-Study Screening Procedure and Initial Assessments: After an initial phone screen to determine obvious exclusions from the study protocol, potential subjects will be invited for a clinic pre-screen and personally interviewed. All subjects will have an initial screening assessment that includes a complete medical history, physical examination, laboratory testing, HIV and Hep B & C testing, psychiatric history, and standardized psychiatric and cognitive assessments.

C.1. Historical and Demographic Information: Each subject will complete a demographic form containing commonly information that is routinely assessed in biomedical research protocols. Specifically, this document will elicit information about the subjects' demographics, including education level, socioeconomic status, race and ethnicity. In addition, it will also request information on the subject's family history of mental illness.

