viewing the pictures at any time during the testing and still continue in the study. Participants may be asked to return for a repeat session due to inadequate image acquisition or time constraints. No more than three repeat sessions will be attempted.

4. Genetic Testing N/A

A. Describe

- i. the types of future research to be conducted using the materials, specifying if immortalization of cell lines, whole exome or genome sequencing, genome wide association studies, or animal studies are planned
- ii. the plan for the collection of material or the conditions under which material will be received
- iii. the types of information about the donor/individual contributors that will be entered into a database
- iv. the methods to uphold confidentiality

B. What are the conditions or procedures for sharing of materials and/or distributing for future research projects?

C. Is widespread sharing of materials planned?

D. When and under what conditions will materials be stripped of all identifiers?

E. Can donor-subjects withdraw their materials at any time, and/or withdraw the identifiers that connect them to their materials?

- i. How will requests to withdraw materials be handled (e.g., material no longer identified: that is, anonymized) or material destroyed)?

F. Describe the provisions for protection of participant privacy

G. Describe the methods for the security of storage and sharing of materials

5. Subject Population: Provide a detailed description of the types of human subjects who will be recruited into this study.

Twenty-four healthy subjects, between the ages of 21-65 will be recruited. Subjects will be accepted into the protocol after an opportunity to review and provide voluntary written informed consent (see attached) and completion of an extensive medical and psychiatric history, physical examination, mental status examination and routine laboratory assessments. Participants will be enrolled if they meet the inclusion criteria mentioned below (see section 7). Additional demographic, diagnostic and other clinical data, including family psychiatric and substance misuse history and treatment history will be obtained during the face-to-face clinical assessment. All such data will be recorded in written and/or electronic format(s).

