The sample size (n=32) was selected based on previous reports¹³. fMRI processing and GBC analyses will be conducted as previously reported¹⁰⁰. A paired t-test will be conducted to examine the effects of ketamine on GBC (Aim 1). A linear mixed model will examine the effects of ketamine and ketamine-by-lamotrigine interaction on cortical glutamate levels. Delta glutamate (during infusion minus baseline) will be correlated with delta GBC (post infusion minus baseline) (Aim 2). A t-test will compare delta GBC between the lamotrigine and placebo groups (Aim 3). Similar analyses will be conducted to examine the effects of ketamine and lamotrigine on the secondary outcomes, i.e. gln level, gaba level, cortical thickness, subcortical ROIs volumes, fractional anisotropy and mean diffusion, and amygdala activation.

SECTION VI: RESEARCH INVOLVING DRUGS, BIOLOGICS, RADIOTRACERS, PLACEBOS AND DEVICES
--

If this section (or one of its parts, A or B) is not applicable, state N/A and delete the rest of the section.

A. DRUGS, BIOLOGICS and RADIOTRACERS

1. **Identification of Drug, Biologic or Radiotracer:** What is (are) the **name(s)** of the drug(s) biologic(s) or radiotracer(s) being used? Identify whether FDA approval has been granted and for what indication(s).

I. Ketamine has U.S. Food and Drug Administration (USFDA) approval as the only anesthetic for diagnostic and surgical procedures that do not require skeletal muscle relaxation. Ketamine is also indicated for anesthesia induction prior to the administration of other general anesthetic agents or to augment low potency anesthetics such as nitrous oxide.

II. Lamotrigine has U.S. Food and Drug Administration (USFDA) approval as an anticonvulsant. It is also indicated for use in bipolar disorder.

All protocols which utilize a drug, biologic or radiotracer **not** approved by, but regulated by, the FDA, or a radiotracer regulated by the RDRC, must provide the following information:

a. What is the Investigational New Drug (IND) **number** assigned by the FDA?

Not applicable.

b. Who holds the IND?

Not applicable.

c. All protocols which utilize a radiotracer not approved by, but regulated by the FDA must provide the IND number: _____

Alternatively, use of the investigational radiotracer may be under RDRC/RSC oversight: (check if appropriate) _____

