Non-Significant Risk (NSR) Device Study: A study of a device that does not meet the definition for a significant risk device and does not present a potential for serious risk to the health, safety, or welfare of participants. Note that if the HIC concurs with this determination, an IDE is not required.

6. **Abbreviated IDE or Exempt IDE:** There are abbreviated requirements for an IDE and there also are exemptions to the requirement for an IDE. *See the criteria in the HIC Application Instructions, Section VI.B.4 at http://www.yale.edu/hrpp/resources/docs/100FR1aHICProtocol_Application_Instructions5-25-11.pdf to determine if these pertain to this study.*

Abbreviated IDE or Exempt IDE – *If criteria set forth in the HIC Application Instructions are met, copy and paste the completed relevant section from the Instructions into this application.*

7. **Investigational device accountability:**

- a. State how the PI, or named designee, ensures that an investigational device is used only in accordance with the research protocol approved by the HIC, and maintains control of the investigational device as follows:

Maintains appropriate records, including receipt of shipment, inventory at the site, dispensation or use by each participant, and final disposition and/or the return of the investigational device (or other disposal if applicable):

Documents pertinent information assigned to the investigational device (e.g., date, quantity, batch or serial number, expiration date if applicable, and unique code number):

Stores the investigational device according to the manufacturer's recommendations with respect to temperature, humidity, lighting, and other environmental considerations:

Ensures that the device is stored in a secure area with limited access in accordance with applicable regulatory requirements:

Distributes the investigational device to subjects enrolled in the IRB-approved protocol:

SECTION VII: RECRUITMENT/CONSENT AND ASSENT PROCEDURES

- 1. Targeted Enrollment: Give the number of subjects:**
- a. targeted for enrollment at Yale for this protocol: 32
 - b. If this is a multi-site study, give the total number of subjects targeted across all sites _____

- 2. Indicate recruitment methods below.** Attach copies of any recruitment materials that will be used.

- | | | |
|---|--|-------------------------------------|

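### The protocol gives two totals for the same randomised study, 24 in three places and 32 in three others, and nothing reconciles them

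*Combined protocol and SAP*

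**What the plan says.** Six places in the combined protocol and SAP give a total for the same two-group study in healthy volunteers.

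Three give 24:

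- Section V, 1, Aim 1 design: "Twenty-four healthy participants will be randomized into one of two parallel groups"
- Section V, 3.B, Experimental Subjects: "Twenty-four healthy subjects between the ages of 21-65 years will be recruited for this study"
- Section V, 5, Subject Population: "Twenty-four healthy subjects, between the ages of 21-65 will be recruited"

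Three give 32:

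- Section V, 3.A, Overview: "In this study, 32 healthy participants will be randomized into one of two parallel groups"
- Section V, 12, Statistical Considerations: "The sample size (n=32) was selected based on previous reports"
- Section VII, 1, Targeted Enrollment: "targeted for enrollment at Yale for this protocol: 32"

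Sections 3.A and 3.B follow one another directly and carry different numbers. The only basis given for the sample size is the reference to earlier reports in Section V, 12. No significance level, power, effect size, standard deviation or attrition rate is stated there or elsewhere. The Aim 3 design says "Participants will be randomized to receive 300 mg oral lamotrigine or a matched-placebo medication" and gives no allocation ratio.

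**The concern.** Readers of different sections take away different studies. The aims and the description of the population lead to 24; the overview, the statistical section and the enrolment target lead to 32.

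Two things depend on the answer. The first is exposure. Every participant receives ketamine, with lamotrigine or placebo. Section V, 11 rates the study as moderate risk, and Section IX states that participants gain no direct clinical benefit, so the number to be exposed should not be open to interpretation. The second is what the lamotrigine comparison (Aim 3) can detect, which is noticeably weaker with 24 than with 32.

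**Working it through.** **Can the stated figure be reproduced?** No. With no significance level, power, effect size, SD, allocation or dropout given, neither 32 nor 24 can be rebuilt. The check is therefore whether any reading lets both numbers stand.

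**Readings that might reconcile them**

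1. *32 enrolled, 24 completing.* This needs attrition of 1 − 24/32 = 25%, since 24/(1 − 0.25) = 32. Other rates do not reach 32: 24/0.90 gives 27, 24/0.85 gives 29 and 24/0.80 gives 30 (each rounded up). No attrition figure appears. The wording also rules it out: the Aim 1 design and the Overview both speak of randomisation into two parallel groups, one with 24 and the other with 32, and Sections 3.B and V, 5 describe 24 as recruited, which is fewer than 32 randomised.
2. *Replacement of dropouts.* Section V, 3.B.2 says "Subjects may be discontinued from study treatment and assessments at any time" and lists reasons, but has no replacement rule. Failed or incomplete scans are repeated in the same participant (the MRS and MRI methods in Section V, 3, and the payments text in Section X, 2), which adds nobody.
3. *More than one site.* In Section VII, 1 the figure of 32 is the Yale target, and the total across sites is blank.
4. *A subset of 24 for Aim 1.* Sections 3.B and V, 5 present 24 as the whole study population, and the Overview has all participants completing both resting-state scans.

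None of these works.

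**Size of the gap.** 32 − 24 = 8 participants, and 8/24 = 33%.

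**What it does to Aim 3 (illustration).** Section V, 12 plans a t-test of the change in global brain connectivity (GBC) between lamotrigine and placebo. Assumptions, none stated in the protocol: two-sided 5% level, 1:1 allocation, no losses, GBC reduced to one value per person. With n per arm and a standardised difference d, the test has 2n − 2 degrees of freedom and noncentrality d·√(n/2). The detectable d is the value at which noncentral-t power reaches the target.

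| | N = 24 (12 + 12) | N = 32 (16 + 16) |
|---|---|---|
| Degrees of freedom | 22 | 30 |
| Detectable d, 80% power | 1.197 | 1.024 |
| Detectable d, 90% power | 1.385 | 1.185 |
| Power at d = 1.024 | 0.669 | 0.800 |
| Power at d = 1.0 | 0.649 | 0.781 |

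For the third row, the noncentrality at d = 1.024 is 1.024 × √6 = 2.51 with 12 per arm and 1.024 × √8 = 2.90 with 16 per arm.

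**The case against.** The strongest reply is that the six places do not carry equal weight. The two sections whose job is to fix the number, Statistical Considerations and Targeted Enrollment, both say 32, and so does the Overview. The 24s sit in descriptive text and may be left over from an earlier plan. The section that defines the Aim 3 test is then consistent within itself, and no stopping rule, interim look or stated power depends on the total. On that view this is an editing slip.

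It is fair to say that 32 is the likelier intention. It remains an inference, because the text never says that 24 was superseded, and leftover text would still be a contradiction in the current plan about a core design figure.

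Two narrower points stand:

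- The SD figures are illustrative. The background section defines GBC voxel by voxel and describes voxel-wise tests for the pilot data. If Aim 3 is tested that way with correction, the detectable differences are larger. At a two-sided level of 0.001, for example, they are 1.93 SD with 24 and 1.61 SD with 32 at 80% power. The ordering is unchanged.
- Some pages, including the consent form, were not available for this review, so six is the count in the text at hand. A further mention elsewhere could show which number is current but could not make these six agree.

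**Conclusion.** The concern holds. The current text gives two incompatible totals, three mentions each, and no reading of the documents reconciles them. The contradiction rests on wording alone and needs no assumption. The total sample size is a figure the trial relies on, so this must be corrected.

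The gap is eight participants. Under the assumptions set out above, a true Aim 3 difference of 1.02 SD would have 80% power with 32 participants and 67% with 24. Those power figures show why the choice matters; they do not establish which number is right, and the documents available do not settle that.

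**What to change.** The sponsor should confirm the intended randomised total and use it throughout.

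- If it is 32, correct the Aim 1 design in Section V, 1, Section V, 3.B and Section V, 5.
- If it is 24, correct Section V, 3.A, Section V, 12 and Section VII, 1, and check that the appeal to previous reports in Section V, 12 supports 24.

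In either case, state the allocation ratio and the number per arm (16 or 12 if allocation is 1:1), and check the consent form and any other page that quotes a total.

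The cost is a wording amendment at three places plus the per-arm statement. The listed analyses do not change, and if 32 is the intended number no participants are added.

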As noted above, lamotrigine is an anticonvulsant drug. It is also used in the treatment of bipolar disorder, specifically in the treatment and prevention of bipolar depressive episodes ⁷⁸. It is a use-dependent sodium channel blocker and phenyltriazine derivative, which has been demonstrated to possess multiple mechanisms of action ^{79,80}. Briefly, these include the selective blockade of the N- and P-type calcium channels in focal brain regions, and the voltage-dependent blockade of sodium channels via its action on the slow inactivation state that occurs when sodium channels are over-activated. This drug has also been shown to inhibit the release of excitatory amino acids such as glutamate and aspartate, and may have some agonistic effects on γ -aminobutyric acid (GABA). It selectively suppresses neuronal over-activities without affecting the basal neurophysiological state, which has clear implications in neuronal stabilization, and may also be a plausible explanation of its action in bipolar disorder, even though the pathophysiology of this condition is less clear ⁷⁹. Lamotrigine is also believed to act on serotonin reuptake, which may contribute to its antidepressant effects ^{79,81}. There is evidence of peripheral glutamate dysregulation in bipolar disorder ⁸², and the glutamatergic activity of lamotrigine may also be implicated in its therapeutic and neuroprotective effects. Lamotrigine levels have been shown to peak at 1 to 4 hours after oral administration, with a mean of 2 hours.

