28. *Socio-demographic/General Information*: At intake, demographic data and medical history will be assessed with interviews and self-report forms that provide data on age, race, socioeconomic status, marital status, educational and

occupational levels, and significant medical history. These are adapted from previous diagnostic and clinical studies at this center.

D.3. Biochemical Analyses: 10 mL of blood are drawn for the analysis of ketamine levels. Plasma ketamine levels are ascertained via a gas chromatography-mass spectroscopy assay developed by [name] M.D. ⁹⁵.

E. *Lamotrigine Administration:* Subjects randomized to the active lamotrigine group will receive a 300 mg oral dose of the drug 2-hours prior to the start of the ketamine-infusion. Lamotrigine levels will be measured using commercially available radioimmunoassay kits.

A physician who is trained and has experience with lamotrigine and possible allergic and other adverse events will remain in attendance at all sessions that involve drug administration.

F. *Ketamine Administration:* Subjects will complete one test day. Following an overnight fast, IV lines will be inserted into the antecubital vein. They will receive ketamine (0.23mg/kg bolus followed by 0.58mg/kg infusion over approximately 60 minutes).

A physician who is trained and has significant experience with both ketamine and infusion studies will remain in attendance at all sessions that involve ketamine infusion. The subjects will also be attended by a nurse who will accompany them through the study sessions, from the insertion of bilateral cannulae for drug infusion and blood sampling, through to recovery following ketamine infusion.

Baseline Test Session (Test Session 1 Day-0)

- T -15 min: Urine toxicology; Urine pregnancy test (women only);
Breathalyzer; MRI Safety Data Sheet; Metal Detector
- T -0 min: rs-fMRI (and other imaging protocols on the 3T scanner)
- Post fMRI Brief neuropsychological battery

Test session 1 (Day #1)

- T -120 min: Vital signs *; Urine toxicology; Urine pregnancy test (women only); Breathalyzer; PSWQ, PSQI, MRI Safety Data Sheet; Metal Detector; Lamotrigine or matched-placebo control administration
- T-90 min: Intravenous lines started
- T -45 min: MRS setup and baseline scan
- T-0 min: Ketamine infusion begins (0.23mg/kg bolus followed by 0.58mg/kg infused over 60 minutes)
- T 5-75: MRS acquisition continues

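### Aim 2 correlates the glutamate and GBC changes with no term for randomised arm, so a pooled r can turn positive from lamotrigine's separate effects on the two measures

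*Combined protocol and SAP*

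**What the plan says.** Section V, item 12 (Statistical Considerations) gives Aim 2 one sentence on the correlation: "Delta glutamate (during infusion minus baseline) will be correlated with delta GBC (post infusion minus baseline) (Aim 2". The Aim 2 text in Section V, item 1 (Statement of Purpose) speaks of healthy subjects, which fits both arms, and names no arm. Its hypothesis is directional: "Ketamine-induced glutamate alterations will positively correlate with changes in GBC".

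Both randomised groups receive ketamine and differ only in lamotrigine or placebo. For connectivity, Hypothesis 3 states: "Lamotrigine will attenuate the effect of ketamine-induced GBC enhancement in the neural network". For glutamate, no hypothesis gives a direction for the spectroscopy measure, but the Background section says of lamotrigine: "This drug has also been shown to inhibit the release of excitatory amino acids such as glutamate and aspartate". The Background summary adds that "use of lamotrigine will allow us to confirm target engagement and the impact of blocking the glutamate system".

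Item 12 also plans a mixed model for cortical glutamate with a ketamine-by-lamotrigine term, and a t-test of delta GBC between arms (Aim 3). Neither is part of the Aim 2 correlation.

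**The concern.** The trial randomises a drug that is meant to lower one of the two correlated variables and that plausibly lowers the other. When two groups are pooled, r mixes the association inside each group with the association between the group means. If lamotrigine lowers both deltas, the lamotrigine cloud sits below and to the left of the placebo cloud. The pooled r is then pulled upwards even if, within each arm, a participant's glutamate change says nothing about that participant's connectivity change.

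A positive pooled r would look like support for Hypothesis 2, and it would be easy to read it as evidence that glutamate and connectivity move together within people. Two separate effects of the randomised drug would produce the same result. The sentence in item 12 is also compatible with pooled, placebo-only, within-arm or adjusted analyses, so the choice stays open until the data are seen.

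**Working it through.** **Inputs from the documents.** Two parallel arms; N=32 (item 12, Overview, targeted enrolment) or N=24 (aims, subject sections). That conflict is a separate matter, so both values are carried. The plan gives no alpha, power, SD or effect size for Aim 2, so there is no planned figure to reproduce.

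**Assumptions.** 1:1 allocation, bivariate normal data, equal within-arm variances, a common within-arm correlation r_w, one scalar GBC summary, both deltas available for everyone, Pearson r tested two-sided at 5%. Shifts sx (delta glutamate) and sy (delta GBC) are between-arm differences in within-arm SDs. They are a range, not estimates.

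**Expected pooled correlation with equal arms:**

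r_pooled = (r_w + sx·sy/4) / √[(1 + sx²/4)(1 + sy²/4)]

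With r_w = 0:
- 0.5/0.5: 0.0625/1.0625 = 0.059
- 0.5/1.0: 0.125/√(1.0625 × 1.25) = 0.108
- 0.8/0.8: 0.16/1.16 = 0.138
- 1.0/1.0: 0.25/1.25 = 0.200
- either shift zero: 0

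**False-positive rates with r_w = 0** (200,000 simulated trials per row; pooled test on N−2 df, arm-adjusted test on N−3 df):

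| Shift, glutamate/GBC (SD) | Pooled, N=32 | Pooled, N=24 | Arm-adjusted |
|---|---|---|---|
| only one measure shifts | 5% | 5% | about 5% |
| 0.5/0.5 | 6.3% | 5.9% | about 5% |
| 0.5/1.0 | 9.1% | 8.0% | about 5% |
| 0.8/0.8 | 11.8% | 10.0% | about 5% |
| 1.0/1.0 | 20.0% | 15.7% | about 5% |

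The excess is almost all in the positive tail. At 1.0/1.0 and N=32, 19.9% of trials give a significant positive r and 0.1% a significant negative one.

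**Power when a link exists, r_w = 0.5:**
- No arm effect: pooled 85.2%, adjusted 84.0% (N=32); 73.1% and 71.1% (N=24).
- GBC alone shifts by 1 SD: r_pooled = 0.5/√1.25 = 0.447. Power is 74.7% pooled and 84.1% adjusted (N=32); 60.8% and 71.0% (N=24).
- Lamotrigine's GBC effect runs through glutamate (1 SD glutamate shift, hence 0.5 × 1 = 0.5 SD in GBC): r_pooled = 0.625/√(1.25 × 1.0625) = 0.542. Power is 91.6% pooled and 84.0% adjusted (N=32); 81.7% and 71.1% (N=24).

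**Precision of the candidate estimates**, for an observed r of 0.5, by Fisher z (atanh 0.5 = 0.549):
- arm-adjusted, N=32: SE 1/√28, 95% CI 0.18 to 0.73
- one arm, n=16: SE 1/√13, 95% CI 0.01 to 0.80
- one arm, n=12: SE 1/√9, 95% CI −0.10 to 0.83

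**The case against.** **Hypothesis 2 says only that the changes correlate, and a pooled r describes that.** This stands. Lamotrigine is there partly to perturb glutamate, and an arm term discards the variation it induces. Under mediation the adjusted test loses power, as shown above. This is a reason to keep the pooled r. It is not a reason to let it carry, alone, a claim about a glutamate–connectivity link.

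**Other planned analyses would show the arm effects.** Largely true where it matters. With two-sample t-tests at 5% standing in for the mixed model and the Aim 3 test, at N=32 at least one arm difference is also significant in about 99% of falsely significant pooled results at 1.0/1.0, 92% at 0.8/0.8, 91% at 0.5/1.0 and 57% at 0.5/0.5. That warns the reader but does not remove the shift from r.

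**The magnitudes are assumed.** Also true. GBC processing is delegated to a cited report, and voxel-wise maps with cluster control would behave differently. A common within-arm r and equal variances are questionable if lamotrigine blunts the glutamate response.

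**Inferences the documents do not support.**
- A reader might infer that the glutamate shift cancels because the spectroscopy baseline ("T -45 min: MRS setup and baseline scan") follows the capsule (at T −120 min: "Lamotrigine or matched-placebo control administration"), while the imaging baseline is about a week earlier. But ketamine starts only at T 0, so blunting of its effect cannot already be present at T −45. The Background also describes lamotrigine as leaving basal neurophysiology unaffected.
- A reader might expect the shifts to have opposite signs, which would mask a real link. That runs against the plan's rationale. The result cited in the Background, that lamotrigine increased ketamine's mood-enhancing effect, concerns mood, not connectivity.
- A reader might say that a GBC-only shift hides a real link. It dilutes it, from 0.50 to about 0.45.

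**Conclusion.** The point holds as a conditional one. Aim 2 as written has no arm term. If the arms are pooled and lamotrigine lowers both deltas, r gains a positive component in the hypothesised direction that reflects randomisation alone. The false-positive rate is barely raised for 0.5 SD shifts (about 6%) and reaches 20% at N=32, or 16% at N=24, for 1 SD shifts in both measures. With a GBC-only shift the issue is lost power, not false positives. All of this rests on the assumptions listed in the working.

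A reader might infer that the pooled correlation is invalid or that a positive result will be spurious. The documents do not support that. They give no size for either shift and do not give a direction for spectroscopy glutamate; they also describe that measure as total glutamate, which may reflect processes other than neurotransmission. Nor do they state outright that the arms will be pooled. This is an inexpensive improvement to the plan, not a flaw that undermines the trial.

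**What to change.** In Section V, item 12:

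1. State that Aim 2 uses all randomised participants who have both delta glutamate and delta GBC.
2. Regress delta GBC on delta glutamate plus arm, on whatever GBC summary or map is used. Report the partial correlation with its 95% CI, and base any claim of a glutamate–GBC link beyond arm differences on it.
3. Report the unadjusted pooled correlation beside it, labelled as including between-arm variation.
4. Report the two within-arm correlations with intervals, as description only, given their width.

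No new data, visits or participants are needed. The statistical price is one degree of freedom when there is no arm effect: power at r = 0.5 goes from about 85% to 84% (N=32) or 73% to 71% (N=24). If lamotrigine's GBC effect runs through glutamate the price is higher, about 92% to 84% (N=32) or 82% to 71% (N=24). That is why the pooled r stays in the report.
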